5.1.2 Unscheduled Visits

Additional visits may be scheduled, as necessary, to ensure the safety and well-being of subjects. All additional exams should be fully documented on Unscheduled Visit forms as appropriate.

5.1.3 Missed Visits

If a subject misses a Study Visit, the visit is considered missed and the subject must be exited from the study. The Investigator or designee must check the missed visit box on the first page of the applicable CRF/e-CRF for that visit.

See Section 3.2.4 Lost to Follow-Up for applicable instructions for subjects who do not return for the final visit.

5.1.4 Post-Study Follow-up Visit

There is no planned follow-up period after the clinical investigation is complete. If a subject requires further follow-up upon discontinuation or completion of the study, the Investigator must schedule post-study follow-up visits, as necessary. The Investigator is required to follow the subject until the condition no longer warrants further follow-up for study purposes. A Post-Study Follow-up Visit e-CRF/CRF must be completed for each of these visits.

There will not be any routine eye care provided after the clinical investigation is complete. Subjects should follow-up with their eye care provider every 1-2 years for comprehensive eye care or sooner as recommended by their eye care provider.

5.2 Study Completion

The subject has completed the study when the second visit is concluded. Subjects who require further follow-up will be followed according to the Adverse Event or Post- Study Follow-Up Section. There is no planned follow-up period after the clinical investigation is complete.

The completion of the clinical investigation shall be deemed to coincide with the last visit of the last subject and when follow-up is complete.

5.2.1 Study Termination/Suspension

If during the study it becomes evident that the study should be stopped prematurely or placed on hold, appropriate notification will be given to the requestor and IRB/ECs, as applicable. Should the Investigator and/or study requester wish to terminate the study, the following Research Clinic procedure will be followed. Any subjects with ongoing Adverse

Events at the time of premature study termination or hold will be followed by the Investigator.

5.2.2 Study Termination Procedure

The decision to terminate a study will be made by the Director of Clinical Affairs and the Principal Investigator (PI). A final slit lamp examination should be performed, and adverse events handled accordingly. All investigational materials (lenses, solutions, and / or devices) will be retrieved, all subjects will be exited, and the Trial Master File will be reconciled. A clinical report will be written and include the reason for study termination.

5.3 Concomitant Medications/Therapy

Ocular, systemic or topical medications that, in the Investigator's opinion, could potentially affect ocular physiology or lens/solution performance are prohibited.

5.4 Protocol Deviations

The date of and reason for deviations will be documented in all cases. Significant or major protocol deviations impacting the safety of the subject or the integrity of the study must be reported by the Investigator to the IRB immediately. Reporting of all other protocol deviations must adhere to the requirements of the governing IRB/EC.

Any subject enrolled in the study who later is found to have not met the eligibility criteria at entry will be discontinued. Otherwise, unless the protocol deviations put the subject at risk or the subject's condition requires that they be discontinued from the study, subjects may continue to participate until the end of the study.

6.0 ADVERSE EVENTS (AE)

Subjects who experience an adverse event during study participation will be discontinued from study participation, but will be followed by the Investigator until resolution of the adverse event or until the Investigator determines that further improvement is not expected.

6.1 Adverse Event Definitions

For the purposes of this study, reportable AEs include ocular AEs and non-ocular serious adverse events (SAEs). All AEs will be classified first for seriousness and significance and then as to whether or not they are device related or non-device related and if device related, then, if it is an adverse device effect (ADE), an anticipated serious adverse device effect (ASADEs) or an unanticipated serious adverse device effect (USADEs). AEs, ADEs, ASADEs, USADEs, SAEs, Significant Non-Serious AEs and Non-Significant Non-Serious AEs are defined as follows:

6.1.1 Adverse Event (AE)

Any untoward medical occurrence, unintended disease or injury, or untoward clinical signs (including abnormal laboratory findings) in subjects or users, whether or not related to the investigational medical device. Adverse events should be categorized as device related or non-device related.

Throughout the course of this study all efforts will be made to remain alert to reportable

AEs. If an AE occurs, the first concern will be the safety of the subject and appropriate medical intervention will be made.

All reportable AEs occurring after signing of informed consent and through the subject's end of participation in the study must be reported. All reportable AEs must be followed until the event resolves or stabilizes.

6.1.2 Serious Adverse Event (SAE)

An adverse event which:

- Led to death;
- Led to serious deterioration in the health of the subject, that resulted in:
 - A life-threatening illness or injury; or
 - A permanent impairment of a body structure or a body function (e.g., blindness); or
 - Inpatient or prolonged hospitalization; or
 - Medical or surgical intervention to prevent life-threatening illness or
 - Injury or permanent impairment to a body structure or a body function;
- Led to fetal distress, fetal death, or a congenital abnormality or birth defect.

6.1.3 Serious Adverse Ocular Event

Serious Adverse Ocular Event is a serious adverse event that results in, or has potential to cause, either permanent impairment of an ocular function or damage to an ocular structure and may necessitate medical or surgical intervention. Serious Adverse Events require expedited reporting. Serious adverse events include any hazardous, **sight-threatening conditions** occurring after exposure to a test article, including but not limited to the following:

- A presumed infectious ulcer (defined as a progressive erosion of the corneal tissue). For the purposes of reporting, a corneal ulcer which has *any* of the following characteristics should be considered in this category:
 - Central or paracentral location;
 - Penetration of Bowman's membrane;
 - Infiltrate ≥ 2 mm diameter;
 - Associated with iritis;
 - Associated with any increase in intraocular pressure;
 - Culture positive for microorganisms;
 - Increasing size or severity at subsequent visits.

Note: Signs of a presumed infectious ulcer may include irregular focal infiltrates; active lesions with raised edges; significant diffuse infiltration; anterior corneal to mid-stromal involvement; erosion with overlying staining; conjunctival and lid edema; anterior chamber reaction (iritis); severe bulbar and limbal redness.

Symptoms associated with a presumed infectious ulcer (microbial keratitis) may include pain of rapid onset; severe redness; purulent or mucopurulent discharge; tearing; photophobia.

- Any central or paracentral (within 6 mm of cornea) corneal event that results in permanent opacification (such as corneal scar or vascularization)
- Any serious adverse ophthalmic events including hypopyon and hyphema.
- Any neovascularization within the central 6 mm of the cornea.
- Permanent loss of 2 or more lines (10 letters) of BSCVA.
- All cases of iritis.

6.1.4 Significant, Non-Serious Adverse Event

A Significant, Non-Serious Adverse Event is an Adverse Event that does not meet the serious criteria, is considered significant, and requires expedited reporting. These events include (but are not limited to):

- Peripheral non-progressive non-infectious corneal ulcer
- All symptomatic corneal infiltrative events
- All cases of corneal staining severity greater than or equal to Grade 3
- A temporary loss of 2 or more lines (10 or more letters) of BSCVA (for greater than or equal to 2 weeks)
- Increase in neovascularization of 1.5mm or greater.
- Any ocular event that necessitates temporary lens discontinuation of greater than or equal to 2 weeks.

6.1.5 Non-significant, Non-serious Adverse Event

A Non-Significant Non-Serious Adverse Event may include (but are not limited to) and does not require expedited reporting:

- Asymptomatic, peripheral, corneal infiltrative events.
- Bacterial Conjunctivitis
- Viral Conjunctivitis
- Allergic Conjunctivitis
- Corneal Edema
- Contact Lens Related Papillary Conjunctivitis

6.1.6 Adverse Device Effect (ADE)

An ADE is an Adverse Event that is assessed to be related to the use of an investigational medical device. This definition includes Adverse Events resulting from insufficient or inadequate instructions for use; deployment, implantation, installation, or operation; or any malfunction of the investigational medical device. This definition also includes any event resulting from use error or from intentional misuse of the investigational medical device.

6.1.6.1 Anticipated Serious Adverse Device Effect (ASADE)

An ASADE is an ADE that first meets the serious criteria (see definition above for Serious Adverse Event) or significant, non-serious criteria (see above definition for significant, non-serious AE) and which, by its nature, incidence, severity or outcome, has been previously identified in the investigational plan or application (including a supplementary plan or application) and/or in the risk analysis report. ASADEs include:

- Corneal Ulcer (infectious or non-infectious)
- Keratitis
- Sensitivity to light (photophobia)
- Excessive eye secretions including mucopurulent discharge
- Blurred vision, rainbows or halos around objects
- Poor visual acuity (reduced sharpness of vision)
- Moderate to severe eye pain not relieved by removing the lens

6.1.6.2 Unanticipated Serious Adverse Device Effect (USADE)

An USADE is an ADE that first meets the serious criteria (see definition above for Serious Adverse Event) or significant, non-serious criteria (see above definition for significant, non-serious AE) and has an effect on health or safety or any life-threatening problem or death caused by, or associated with, a device if that effect, problem or death was not previously identified in nature, severity or degree of incidence in the investigational plan or application (including a supplementary plan or application), or any other unanticipated serious problem associated with a device that relates to the rights, safety, or welfare of subjects.

6.1.7 Device Deficiency

Inadequacy of an investigational medical device with respect to its identity, quality, durability, reliability, safety, or performance. This includes malfunctions, use errors, inadequate labelling, insufficient or inadequate instructions for use. A Device Deficiency can occur with or without the occurrence of an Adverse Event.

6.2 Adverse Event Treatment and Culturing

With any Adverse Event, treat the subject as appropriate to prevent further complications and to potentially resolve the event consistent with the standard of care.

A culture should be obtained in cases of corneal ulcer or suspected ocular infection, unless medically contraindicated. Cultures should be taken from the cul-de-sac, lower eyelid margin, and the corneal lesion (if applicable). When a culture is obtained, the contact lenses and contact lens cases which were being utilized by the subject at the time of the AE should be collected from the subject (if available at the time of the culture) for culturing and processing by the clinical laboratory designated by the Research Clinic. Microbial data generated from returned subject supplies (e.g., lenses, lens cases and/or lens case solutions) are for information only. Because microbes may be introduced into subject supplies during use, recovery of microbes from returned subject supplies cannot be presumed to indicate etiology or direction of organism transmission. The ocular cultures, along with the associated contact lenses and contact lens cases, will be sent to the clinical laboratory designated by the Research Clinic for analysis. The clinical laboratory will report the culture results to both the Investigator and to the Research Clinic, the Investigator will record the results in the applicable form.

6.3 Adverse Event Identification and Evaluation

Throughout the course of a study all efforts will be made to remain alert to Adverse Events

(AEs). If an AE occurs, the first concern will be the safety of the subject and appropriate medical intervention will be made. The associated product should be retained for further analysis, if needed.

All AEs occurring after signing the informed consent and through the end of the subject's participation in the study must be recorded and reported, if applicable. All AEs must be followed until the event resolves or stabilizes.

Identify potential adverse events during a clinical study by using the following sources:

- Direct observation by the Investigator
- Asking the study participant using a non-specific question (i.e. Have you had any problems since the last visit?)
- Unsolicited volunteering of information by the study participant (i.e. Doctor, I have had numerous headaches since I started using this lens)
- Laboratory or test results that meet protocol requirements for classification as an adverse event (i.e. IOP over 30mmHg)
- When evaluating AEs, the Investigator should classify the AE based on the following three criteria:

1. **Seriousness and/or significance** (based on the criteria provided in Section 6.1)

Severity:

- Mild: Subject awareness of a sign or symptom that is easily tolerated, requires no treatment, and does not interfere with subject's daily activities.
- Moderate: Subject awareness of a sign or symptom which may be a low level of concern to the subject and may interfere with daily activities but can be relieved by simple therapeutic care.
- Severe: A sign or symptom that interrupts the subject's daily activity and requires systemic therapy or other treatment.

2. **The relationship of the event to the study device** using the following guidelines:

- **Related:** There is at least a reasonable possibility that the AE is related to the study device (contact lens) and/or solution or rewetting drops. Reasonable possibility means that there is evidence to suggest a causal relationship or association between the study device and/or solution or rewetting drops and the AE. Also referred to as an ADE.
- **Not Related:** There is little or no reasonable possibility that the AE is related to the study device (contact lens) and/or solution or rewetting drops. This assessment implies that the AE has no evidence to suggest either a causal relationship or association to the study device and/or solution or rewetting drops and a more likely or certain alternative etiology exists.

3. **Expectedness** of the event

- **Unexpected Adverse Event (UAE):** Unexpected Adverse Events must be reported to the IRB within 10 calendar days of discovery.

- Expected Adverse Event: An adverse event of which, the nature or severity of which is consistent with the current product labeling, investigator brochure, data sheet, etc.

6.4 Adverse Event Collection and Reporting

The Research Clinic will delegate each function's roles and responsibilities related to adverse event reporting. The Director of Clinical Affairs is responsible for ensuring that all Research Clinic Staff understand their responsibilities for collecting and assessing adverse event information and forwarding applicable adverse event information to the appropriate business function.

Research Clinic Staff are responsible for understanding the procedures for adverse event collection, evaluation, documentation, and reporting.

- Collect and record information about any identified adverse event (including the date of the adverse event, treatment, resolution, assessment of both the seriousness and the relationship to the investigational device and the related procedure) on the Adverse Event form. The Adverse Event Form will be completed each time the subject is seen during the management of the incident and at resolution of the incident.
- If an adverse event is determined to be serious or significant and non-serious, notify the Principal Investigator immediately.
- Report all serious or significant and non-serious adverse events within twenty-four (24) hours to Regulatory Affairs, Global Product Surveillance and/or Global Safety Surveillance and Pharmacovigilance as appropriate for the product being evaluated. Continue to send follow-up information or provide support to the appropriate reporting business function for any serious adverse event as soon as it becomes available.
- Ensure that the subject's identity is protected and the subject's identifiers in the study are properly documented on the form.
- Report all unexpected adverse device effects to the reviewing Institutional Review Board within 10 business days of discovery. Continue to send follow-up information as soon as it becomes available.
- Report any adverse event resulting from Intentional Misuse of an investigational medical device per the same procedures as above.
- Report any adverse event resulting from a Device Deficiency per the same procedures as above. All Device Deficiencies should be recorded and evaluated for the potential to cause a serious adverse event.
- All appropriate measures will be taken to ensure the safety of the subject. Follow the subject until the adverse event resolves or until an appropriate endpoint is reached. This may imply that follow-up will continue after the subject has left the study.
- A treatment of an AE will depend on the severity of the adverse event. The Principal Investigator will refer the subject to a suitably licensed eye care professional for immediate treatment if necessary.

- Expenses incurred for study-related medical treatment will be paid by Bausch + Lomb. Research Clinic Staff will contact Environmental Health and Safety to initiate the medical payment claims process.
- If it is determined, based on evaluation of any serious adverse event or serious adverse event trending, that the study presents an unreasonable risk, the Research Clinic may choose to terminate the study. Refer to the Study Termination procedures for additional information and relevant periods for terminating a study.
- All adverse events will be documented in the final study report. Adverse Event documentation must be saved in the Trial Master File and in the respective study folder in the electronic repository.

6.5 Reporting Device Deficiencies

- Report to Global Pharmacovigilance and Risk Management (GPRM) and Design Quality within 24 Hours.
- All device deficiencies must be evaluated by the Investigator, and then evaluated by GPRM and Design Quality.
- The Principal Investigator (PI) will record, evaluate, and report via applicable forms any complaints/deficiencies or malfunctions experienced with the study devices using the Device Deficiency form and when applicable, AE form (if AE has occurred). The PI will evaluate the Device Deficiency and record whether an AE occurred related to the device deficiency and also determine the potential of the device deficiency to cause a serious adverse device effect (SADE). The device deficiency form is then sent to GPRM to evaluate as the Sponsor, their independent determination if the device deficiency led to or could have led to a SADE. See ISO 14155:2020 for resolving any discrepancies between the interpretation by the PI and Sponsor on whether the device deficiency could have led to SADE.
 - If there was an Adverse Event that occurred as well as the device deficiency, then it should be reported as both an Adverse Event and a Device Deficiency (both forms should be completed).
 - If the Device Deficiency is unrelated to an Adverse Event, then just the Device Deficiency should be reported on the Device Deficiency form.
- Additionally, the Device Deficiency form will be sent to Bausch + Lomb Design Quality to evaluate whether any updates to Design Records need to be made.

7.0 STATISTICAL METHODS

7.1 Study Endpoints

Primary Endpoint:

1. Normalized logMAR Visual Acuity

7.2 Hypotheses

The null hypothesis is that the difference in mean normalized logMAR VA between the two lens types is 0.05 or greater. The alternative hypothesis is that the difference is less than 0.05.

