Statistical Methods: Continuous data will be summarized using descriptive statistics: n, mean, standard deviation, median, minimum and maximum. Categorical data will be presented by the total counts for each category and corresponding percentages. The data for each of the ordinal dependent measures (i.e., those assigned a clinical grade) will be analyzed using appropriate nonparametric techniques. Unless otherwise noted, paired t tests will be used to test for differences in means for each of the parametric dependent variables. Differences at the $p < 0.05$ level are considered to be statistically significant.

Sample Size Calculations: In a previous study with similar lenses (ROC2-16-032), the standard deviation for logMAR VA was 0.069. A sample size of 15 subjects was calculated to have a study power of 80%.

Table of Contents

INVESTIGATIONAL SITE AND STUDY PERSONNEL.....	2
SYNOPSIS.....	3
1.0 INTRODUCTION	10
2.0 OBJECTIVE	10
3.0 STUDY DESIGN.....	10
3.1 Description of Study Design.....	10
3.2 Selection of Study Population.....	10
3.2.1 Eligibility	11
3.2.1.1 Inclusion Criteria	11
3.2.1.2 Exclusion Criteria	11
3.2.2 Point of Enrollment and Randomization.....	11
3.2.3 Subject Completion.....	11
3.2.4 Lost to Follow-up.....	12
3.3 Investigators.....	12
3.4 Study Duration	12
3.5 Protocol Changes and Amendments	12
4.0 STUDY MATERIALS	13
4.1 Description of the Test Article(s) (Study Lenses)	13
4.2 Description of Comparator Product(s) (Control Lenses).....	13
4.3 Instructions for Use and Administration.....	13
4.3.1 Storage Requirements	13
4.3.2 Subject Instructions.....	13
4.4 Other Study Materials	14
4.5 Packaging and Labeling	14
4.6 Accountability.....	14
4.7 Masking.....	14
4.8 Product Replacement	14
4.9 Risk Assessment	14
4.9.1 Risk Related to Subject.....	15
4.9.2 Risk Related to Data Management	15
4.10 Relevance of Clinical Investigation.....	15
5.0 STUDY METHODS.....	16
5.1 Study Visits	16

5.1.1 METHODOLOGY:	16
5.1.2 Unscheduled Visits	17
5.1.3 Missed Visits.....	17
5.1.4 Post-Study Follow-up Visit	17
5.2 Study Completion	17
5.2.1 Study Termination/Suspension	17
5.2.2 Study Termination Procedure	18
5.3 Concomitant Medications/Therapy.....	18
5.4 Protocol Deviations.....	18
6.0 ADVERSE EVENTS (AE).....	18
6.1 Adverse Event Definitions.....	18
6.1.1 Adverse Event (AE).....	18
6.1.2 Serious Adverse Event (SAE).....	19
6.1.3 Serious Adverse Ocular Event	19
6.1.4 Significant, Non-Serious Adverse Event	20

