5.1 Study Visits

5.1.1 METHODOLOGY:

Visit 1, Insertion

- Subjects will have at least an 8 hour no lens washout period prior to their insertion visit.
- Limbal and bulbar redness, corneal and conjunctival staining will be assessed with the slit lamp.
- Percent area staining covered will be assessed for all 5 quadrants of the cornea.
- A baseline spherical refraction will be performed, through which High Contrast/High Illumination (HCHI) logMAR visual acuity will be measured at 6m.
- Each subject will insert a randomized lens pair.
- Evaluate: sting/burn, dryness, comfort after 3 minutes of lens wear, centration, movement, wettability, deposits and preference based on comfort.
- Spherical over-refraction will be performed through which HCHI logMAR visual acuity will be measured at 6m.
- The subject will be instructed to wear the lens pair for approximately 2 hours.

Visit 2, Follow-up After 2 Hours of Lens Wear

- Spherical over-refraction will be performed through which HCHI logMAR visual acuity will be measured at 6m.
- Evaluate: sting/burn, dryness, comfort, preference for comfort, centration, movement, wettability, deposits and preference based on comfort.
- Limbal and bulbar redness will be re-assessed.
- Lenses will be harvested, stored dry in a standard case.
- Corneal and conjunctival staining will be re-assessed with the slit lamp.

- Percent area staining covered will be assessed for all 5 quadrants of the cornea.
- Digital photos of the cornea, conjunctiva, and lenses in situ may be acquired.

Grading scales for the biomicroscopic evaluations and subject assessments are according to applicable Research Clinic procedures. See Appendix A: Methods of Clinical Evaluation.

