7.3 Sample Size

Previous clinical experience with samfilcon A lenses is useful to provide an adequate sample size for this investigation. Too few subjects will lead to a decrease in study power. The power of a study indicates the chance of making a Type II error (i.e. showing no statistical difference even though a difference actually exists). A study power of 100% would require an infinite number of subjects. In clinical studies it is generally acceptable to use a power as low as 80%, which is a good compromise between number of subjects and the risk of not detecting a true difference that exists. The Type I error rate (i.e. chance of finding a statistical difference that really doesn't exist) is typically set at 5% ($p=0.05$) chance.

In a previous study with similar lenses (ROC2-16-032), the standard deviation for logMAR VA was 0.069. A sample size of 15 subjects was calculated to have a study power of 80%.

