7.6 Statistical Analysis

Continuous data will be summarized using descriptive statistics: n, mean, standard deviation, median, minimum and maximum. Categorical data will be presented by the total counts for each category and corresponding percentages. The data for each of the ordinal dependent measures (i.e., those assigned a clinical grade) will be analyzed using appropriate nonparametric techniques. Unless otherwise noted, paired t tests will be used to test for

differences in means for each of the parametric dependent variables. Differences at the $p \leq 0.05$ level will be considered statistically significant.

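### The paired t test planned for the primary endpoint is not tied to the 0.05 logMAR margin that section 7.2 sets as the null hypothesis

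*Combined protocol and SAP*

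**What the plan says.** - **Endpoint (7.1).** The single primary endpoint is "Normalized logMAR Visual Acuity". No analysis visit is named. Section 5.1.1 has the same entry at both Visit 1 (after insertion) and Visit 2 (after two hours): "Spherical over-refraction will be performed through which HCHI logMAR visual acuity will be measured at 6m".
- **Hypothesis (7.2).** "The null hypothesis is that the difference in mean normalized logMAR VA between the two lens types is 0.05 or greater". The alternative is a difference below 0.05. The section names no test, no direction of subtraction and no absolute value.
- **Test (7.6 and synopsis, Statistical Methods).** Section 7.6 begins "Unless otherwise noted, paired t tests will be used to test for" differences. The synopsis gives the whole clause: "paired t tests will be used to test for differences in means for each of the parametric dependent variables". Significance is set at the 0.05 level, with no mention of sidedness or of the 0.05 logMAR margin. The listed summary statistics include no confidence interval.
- **Error rates and sample size (7.3).** Type I error is described as the "chance of finding a statistical difference that really" is not there, and Type II error as "showing no statistical difference even though a difference actually exists". The previous-study SD is 0.069, and "A sample size of 15 subjects was calculated to have a study power of 80" percent. Planned enrolment is about 30 (3.1).
- **Other sections.** 7.6.1 sets no pass/fail criteria, 7.6.3 plans no sensitivity analysis, and 7.6.4 requires deviations from the plan to be reported.

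**The concern.** The hypothesis and the test put the burden of proof in opposite places. Under 7.2, the trial must produce evidence that the lenses differ by less than 0.05. Under 7.6, it looks for evidence that they differ at all. A p value against zero cannot reject the 7.2 null: a non-significant result does not show that the difference is below 0.05, and a significant one does not show that it is 0.05 or more.

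The practical danger is that non-significance is reported as if it met 7.2. That reading gets easier as the data get noisier or fewer, which is the wrong incentive for a trial meant to show similarity.

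Sidedness, direction of subtraction and primary visit are also open. Because the plan fixes none of them, choosing one after seeing the data would not count as a deviation to be reported under 7.6.4.

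**Working it through.** **Inputs.** Margin 0.05 (7.2); SD 0.069, power 80% and N = 15 (7.3); enrolment about 30 (3.1); 0.02 logMAR per letter (Appendix A, 1.1). Assumptions: 0.069 is the SD of the within-subject difference, differences are normal, and the zero test is two-sided at 0.05. The plan gives no sidedness for the margin test, so it is shown at one-sided 0.025 and 0.05.

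**1. The plan's own N.** Paired normal formula, n = ((z_α + z_power) × SD / 0.05)²:
- z_α = 1.960: ((1.960 + 0.842) × 0.069 / 0.05)² = 14.95, so 15. This reproduces the plan.
- z_α = 1.645: ((1.645 + 0.842) × 0.069 / 0.05)² = 11.77, so 12.

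The first line is the same calculation for a two-sided zero test to detect 0.05 and for a one-sided 0.025 test against a 0.05 margin at true difference 0. N = 15 therefore does not reveal which test was intended. Exact paired t power at 15 is 74.2% for either.

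**2. Cut-offs for the observed mean difference.** SE = 0.069/√n. The zero test is non-significant up to t₀.₉₇₅ × SE. The margin null is rejected below 0.05 − t × SE.

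| n | SE | Zero test non-significant up to | Margin null rejected below (0.025 / 0.05) | Gap in letters |
|---|---|---|---|---|
| 30 | 0.01260 | 2.045 × SE = 0.0258 | 0.0242 / 0.0286 | 0.08 / 0.14 |
| 15 | 0.01782 | 2.145 × SE = 0.0382 | 0.0118 / 0.0186 | 1.3 / 1.0 |

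**3. True difference exactly 0.05 (on the 7.2 null).** By the noncentral t distribution, the zero test is non-significant with probability 1 − 0.9696 = 3.0% at n = 30 and 1 − 0.7422 = 25.8% at n = 15. A margin test would reject the null in 2.5% or 5%, according to its level.

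**4. How often the two tests part company at n = 30.** Simulated, margin test at one-sided 0.025 / 0.05. The true differences 0.01 and 0.02 are illustrative.

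| True difference | Significant, margin met | Non-significant, margin not met | Total |
|---|---|---|---|
| 0 | 3.5% / 4.1% | 1.6% / 0.4% | 5.1% / 4.4% |
| 0.01 | 3.7% / 6.1% | 5.1% / 1.5% | 8.9% / 7.6% |
| 0.02 | 6.3% / 11.9% | 9.3% / 3.1% | 15.6% / 15.0% |

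Totals are from unrounded values. The first column is a coherent result (a small but real difference). The second is where non-significance would be over-read.

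**5. Power of a margin test, true difference 0, n = 30.** One-sided: 97.0% / 98.7%. Two one-sided tests: 93.9% / 97.4%.

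**6. Range for the SD.** Section 7.3 does not say whether 0.069 is per eye or for the paired difference. If per eye, the SD of the difference is 0.069 × √(2(1 − ρ)), where ρ is the between-eye correlation. At n = 30:

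| ρ (assumed) | SD of difference | Zero cut-off | Margin cut-offs (0.025 / 0.05) | Zero test non-significant at true 0.05 | Two one-sided tests, power (0.025 / 0.05 per side) |
|---|---|---|---|---|---|
| 0 | 0.098 | 0.0364 | 0.0136 / 0.0197 | 22.6% | 55% / 73% |
| 0.25 | 0.0845 | 0.0316 | 0.0184 / 0.0238 | 12.1% | 76% / 87% |
| 0.5 | 0.069 | 0.0258 | 0.0242 / 0.0286 | 3.0% | 94% / 97% |

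**The case against.** The best defence is that this is incomplete wording and not a wrong test. A paired t test can be run against any null value, 7.2 supplies one, and 7.6 is a generic sentence that allows exceptions. The error definitions in 7.3 read like tutorial text. That combined reading is possible, but nothing supports it: 7.2 names no test, no exception is noted anywhere, and every sentence that describes what the test is for speaks of detecting a difference.

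The second argument is that little is lost at planned enrolment. At n = 30 and SD 0.069 the cut-offs almost coincide. True differences of 0, 0.01 and 0.02 all satisfy the alternative, so a reader who took non-significance as success there would still be right. At a true 0.05 that reader would be wrong only 3.0% of the time, and the larger figures are for 15 subjects. This stands as arithmetic. But the agreement is an accident of one n and one SD, and it goes if the SD of the difference is larger.

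Third, 7.6.1 sets no pass/fail rule and no section says that non-significance will be read as meeting 7.2, so the harm is conditional. That also stands. A reader could recover a confidence limit from the two means and an exact p value. Even so, having no study-level gate does not explain how the stated null is to be tested.

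Two smaller points are fair. The plan does not define what normalized means, so the sign convention and the conversion to letters are secure only for raw logMAR. The unnamed visit is a separate gap that would remain if the test were corrected.

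**Conclusion.** The concern holds and must be fixed. The test described in 7.6 and the synopsis does not address the null in 7.2, and no other section connects them.

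The consequence depends on n and the SD. With an SD of paired differences of 0.069, which is the reading under which the plan's N of 15 reproduces, treating non-significance as success at a true difference of 0.05 errs 3.0% of the time at 30 subjects and 25.8% at 15. With an SD of 0.0845 to 0.098 it errs 12% to 23% of the time at 30.

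Power is not the difficulty at 30 subjects and SD 0.069, where every form of margin test has about 94% or more. That reassurance does not extend to the larger SDs. The case rests mainly on the wording, which does not depend on the SD.

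**What to change.** In 7.6 and the synopsis, state that the primary analysis tests the 7.2 null on the within-subject Test minus Control difference in normalized logMAR VA, and specify:

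1. **Scale and sign.** Define normalized, and confirm that a positive difference means worse acuity with the Test lens.
2. **Visit.** Name one. Visit 2 fits the two-hour objective in 2.0.
3. **Form of the hypothesis.** The sponsor should say which reading of 7.2 applies. If directional, reject the null when the upper confidence limit is below 0.05. If an absolute difference is meant, use two one-sided tests, so that the whole interval must lie within −0.05 to +0.05.
4. **Level.** State whether 5% is one-sided or two-sided. By the normal formula one-sided 0.025 matches the stated N of 15; one-sided 0.05 gives 12.

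Rewrite the Type I and Type II definitions in 7.3 to match the margin null, and say whether 0.069 is a per-eye SD or the SD of the paired difference. Label any zero-difference p value as not the primary test. No study-level pass/fail gate is needed.

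The cost is protocol and SAP wording, to be settled before results are seen. The confidence limit comes from paired data already planned. No extra subjects are needed if 0.069 is the SD of the difference; if it is per eye, power at 30 should be rechecked.
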